1 ABBREVIATIONS AND DEFINITIONS

Abbreviation	Description
AE	Adverse Event
CFR	Code of Federal Regulations
CRF	Case Report Form
FDA	Food and Drug Administration
GCP	Good Clinical Practice
HIPAA	Health Insurance Portability and Accountability Act
ICF	Informed Consent Form
IRB	Institutional Review Board
ISO	International Organization for Standardization
NA	Not Applicable
NAV	Not Available
ND	Not Done
PHI	Protected Health Information
PI	Principal Investigator
QRI	Quick Reference Instructions
SAE	Serious Adverse Event
UADE	Unanticipated Adverse Device Events
UNK	Unknown

090177e19dd636e3\Approved\Approved On: 25-Jun-2023 03:44 (GMT)

Abbreviation/Term	Description
Adverse Event (AE)	Any untoward medical event that occurs to a subject during a study (with onset after first study-specific procedure), whether or not that event is considered study-related
Case Report Form (CRF)	A printed, optical, or electronic document designed to record all the information required by the protocol to be reported to the Sponsor on each study subject
Food and Drug Administration (FDA)	An agency of the US government responsible for promulgating regulations and guidelines that further define how to comply with the Food, Drug and Cosmetics Act of Congress. The FDA is authorized to grant marketing approval to new drugs and devices.
Good Clinical Practice (GCP)	A standard for the design, conduct, performance, monitoring, auditing, recording, analyses, and reporting of clinical trials that provides assurance that the data and reported results are credible and accurate, and that the rights, integrity, and confidentiality of the trial subjects are protected
Health Care Professional (HCP)	Person responsible for performing critical study-related procedures
Informed Consent (IC)	A process by which a subject voluntarily confirms his/her willingness to participate in a trial, after having been informed of all aspects of the trial relevant to the subject's decision to participate. Informed consent is documented by means of a written, signed, and dated informed consent form.
Informed Consent Form (ICF)	The form prepared by the Investigator/Sponsor and approved by the IRB, which must be signed by a subject before entry in a clinical trial. It is the legal written record that the subject, or his/her representative, agrees to voluntarily participate in the investigation.
Institutional Review Board (IRB)	Any board, committee, or other group formally designated by an institution to review biomedical research involving subjects and established, operated, and functioning in conformance with 21 CFR Part 56
International Conference on Harmonization (ICH)	A committee consisting of US, EU, and Japanese members organized to develop guidelines for the conduct of clinical studies
Investigator	One or more persons responsible for the practical performance of a trial and for the integrity, health, and welfare of the subjects during the clinical study

090177e19ddd636e3\Approved\Approved On: 25-Jun-2023 03:44 (GMT)

Abbreviation/Term	Description
Subject	A research participant, also called a human subject or an experiment, trial, or study participant or subject, is a person who participates in human subject research by being the target of observation by researchers

1.1 SYNOPSIS

[figure not shown]
Protocol Title	Performance Evaluation of the Lucira COVID-19 & Flu Test as Compared to FDA cleared/authorized SARS-CoV-2 and Influenza A&B Assays
Protocol Number	09A-CLI-001
Objective(s)	The primary objective is to evaluate the performance of the Lucira COVID-19 & Flu Test as compared to FDA cleared or authorized SARS-CoV-2 and Influenza A&B Assays.
Number of Subjects	Minimum of 1000 Symptomatic subjects
Number of Sites	Minimum of 3 sites from at least 2 geographically diverse locations
Study Duration	At least 12 weeks

090177e19dd636e3\Approved\Approved On: 25-Jun-2023 03:44 (GMT)

Study Design	
This study is a prospective, multi-center study to evaluate the performance of the Lucira COVID-19 & Flu Test, a real-time RT-LAMP test intended for the qualitative detection and differentiation of RNA from SARS-CoV-2, Influenza A and Influenza B in self-collected nasal swab samples designed to report rapid test results. The Lucira COVID-19 & Flu Test will be compared with a composite reference method for the detection and differentiation of COVID-19, influenza A and influenza B virus in nasal swabs from patients with signs and symptoms of COVID-19 and/or flu-like illnesses.
 
After determining subject eligibility and following the completion of the informed consent process, each subject will receive a unique study identification number.
 
A subject's participation in this study will consist of one study visit. The subject self-collects a nasal swab sample according to Lucira COVID-19 & Flu Test instructions and runs test according to Quick Reference Instruction (QRI).
 
Following the Lucira COVID-19 & Flu Test self-collection will be an additional swab collection for reference method testing. One (1) additional NS specimen will be collected by the health care professional, prepared in Transport Medium, and sent to the reference laboratory as directed by the Study Operations Manual.
 
Each collection component (investigational product and reference method) may have a maximum of two swabs, including retests, for a maximum of four swabs per visit.

Study Population	
Subject demographics including gender, age, education level, employment status, and household income shall be collected.

090177e19dd636e3\Approved\Approved On: 25-Jun-2023 03:44 (GMT)

1.2 SCHEMA

090177e19dd636e3\Approved\Approved On: 25-Jun-2023 03:44 (GMT)

1.3 SCHEDULE OF ACTIVITIES

Procedure	Subject Identification	Enrollment	Swab Collection	Reference Testing
Identify Potential Subjects	X			
Obtain Written Informed Consent	X			
Review Inclusion/Exclusion Criteria	X			
Assign Subject Number to Eligible Subjects		X		
Record Demographics and Baseline Characteristics		X		
Subject self-collects Nasal Swab Sample and starts test running*			X	
Collect Reference Sample			X	
Ship Reference Samples				X
Complete EDC Entries			X	
Adverse Event/Serious Adverse Event Recording			X	

* Subjects 2-13 years old shall have the collection performed by a parent/guardian/adult with their assent

2 INTRODUCTION

The Lucira COVID-19 & Flu Test is a real-time RT-LAMP test intended for the qualitative detection and differentiation of RNA from SARS-CoV-2, Influenza A and Influenza B in self-collected nasal swab samples.

The test consists of a nasal swab, a sample vial the nasal swab sample is placed in to prepare the sample for testing, and a test unit which detects whether SARS-CoV-2, Influenza A, and Influenza B virus is present within the specimen. The Lucira test uses a proprietary, molecular based detection process to detect whether a person is actively shedding the genomic RNA from the SARS-CoV-2, Influenza A, or Influenza B virus.

The purpose of this study is to investigate the Lucira COVID-19 & Flu Test for the in vitro qualitative detection and differentiation of RNA from SARS-CoV-2, Influenza A, and Influenza B in nasal swab specimens from patients suspected of COVID-19 or Influenza A or Influenza B. The primary objective is to test at least 1000 self-collected nasal swab samples for SARS-CoV-2 and Influenza A&B as compared to FDA cleared/authorized SARS-CoV-2 and Influenza A&B Assays.

Data generated collected in this study shall support an FDA and/or other notified body submission(s).

Known Potential Risks

For this study, the risks to human subjects are minimal. Furthermore, the protocol is exempt from IDE according to §812.2(c) of the IDE regulations because it:

- is non-invasive
- does not require an invasive sampling procedure that presents significant risk
- does not by design or intention introduce energy into a subject; and
- is not used as a diagnostic procedure without confirmation by another medically established diagnostic product or procedure.

090177e19dd636e3Approved\Approved On: 25-Jun-2023 03:44 (GMT)

The procedures outlined in this protocol do not involve significant risk to subject safety. Subjects will be provided the Investigator's contact information and will be instructed to notify them of any Adverse Events (AE) they experience during or secondary to specimen collection procedures. For all forms of swab collection, there is a minimal risk for visibly bloody swabs.

Known Potential Benefits

There is no direct benefit for a subject's participation.

3 INVESTIGATIONAL DEVICE

3.1 NAME AND DESCRIPTION OF INVESTIGATIONAL PRODUCT

The Lucira COVID-19 & Flu Test is a rapid, single-use, molecular test for the qualitative detection and discrimination of SARS-CoV-2 viral RNA in nasal swab samples.

3.2 INTENDED USE

The Lucira COVID-19 & Flu Test is a single use real-time RT-LAMP test kit intended for simultaneous rapid qualitative detection and differentiation of RNA from SARS-CoV-2, Influenza A, and Influenza B virus from self-collected anterior nasal (nasal) Swab specimens, in individuals aged 14 years and older (self-collected), or individuals ≥ 2 years (collected by an adult) suspected of respiratory viral infection consistent with COVID-19, Influenza A, and/or Influenza B. Clinical signs and symptoms of respiratory viral infection due to SARS-CoV-2 and influenza can be similar. The Lucira COVID-19 & Flu Test is intended for use as an aid in the differential diagnosis of SARS-CoV-2, Influenza A, and Influenza B, in humans, and is not intended to detect Influenza C.

The SARS-CoV-2, Influenza A, or Influenza B RNA is generally detectable in nasal Swab samples during the acute phase of infection. Positive results are indicative of the presence of SARS-CoV-2, Influenza A, or Influenza B RNA; clinical correlation with patient history and other diagnostic information is necessary to determine patient infection status. Positive results do not rule out bacterial infection or co-infection with other viruses. The agent detected may not be the definite cause of disease.

Persons who test positive with the Lucira COVID-19 & Flu Test should seek follow up care with their physician, or healthcare provider, as additional testing and public health reporting may be necessary.

Negative results do not preclude infection from SARS-CoV-2, Influenza A, and/or Influenza B and should not be used as the sole basis for treatment or other patient management decisions. Negative results must be combined with clinical observations, patient history, and epidemiological information.

This Lucira COVID-19 & Flu Test is intended for self-testing in a non-laboratory setting, or for home use.

Note: This clinical study and study protocol was initiated with the objectives noted in this protocol, namely, to "[...] confirm the Lucira COVID-19 & Flu Test provides similar performance to a high complexity lab molecular diagnostic RT-PR assay(s) with known high sensitivity." While this objective was initially driven by a request by the US FDA, and as such the Intended Use of US product is included here in the protocol, the intent of this study and the potential results of this study are agnostic of any specific market. Any (slight) variability and differences noted in the this Intended Use versus that of the Intended Use(s) approved or authorized any other market is very minor and does not alter the principle mode of action of the device, the intended patient population, or the fundamental Intended Use of the device.

3.3 PRODUCT LABELING

Product will be labeled according to internal procedures and 21 CFR Part 809.10. Investigational material will be labeled minimally Lucira Health's name, expiration date, lot number, storage conditions and the

090177e19dd636e3Approved\Approved On: 25-Jun-2023 03:44 (GMT)

federal caution statement "For Investigational Use Only. The performance characteristics of the product have not been established."

3.4 STORAGE AND HANDLING

All study supplies should be stored in a controlled location with limited access. The Lucira COVID-19 & Flu Test should not be opened until ready to use. Sample vials and test cartridges should be stored in their foil pouches until testing is performed. Sample vials and test cartridges are for a single use only and should not be reused. Test cartridges that have been out of the desiccated pouch for more than 20 minutes should be discarded. None of the test components should be frozen. All study supplies should be stored at room temperature.

4 OBJECTIVES

The primary objective is to confirm the Lucira COVID-19 & Flu Test provides similar performance to a high complexity lab molecular diagnostic RT-PCR assay(s) with known high sensitivity. The sensitivity and specificity endpoint are PPA $\geq 80\%$ /NPA $\geq 98\%$ for COVID-19 and PPA $\geq 90\%$ /NPA $\geq 95\%$ for Flu A&B.

5 STUDY DESIGN

5.1 STUDY DESIGN

The study is a prospective with a minimum of three (3) sites in the U.S. will participate in the study. The Investigational device shall be tested on-site, and the reference samples shall be sent a reference laboratory in the U.S. Testing in the reference laboratory will be performed by trained laboratory personnel. This investigational device testing is to be performed in a simulated-home environment with medical staff on site and shall include nasal swabs self-collected by study subjects per the QRI.

A qualified research person will be designated as the Investigator at each site, with the responsibility for oversight of the study in accordance with Good Clinical Practice (GCP) and regulatory requirements. The protocol and subject informed consent will be reviewed by an Institutional Review Board (IRB) and written IRB approval will be issued prior to enrollment of subjects into the study at that site.

A subject's participation in this study will consist of a single visit. Following completion of the informed consent process and a review of Inclusion/Exclusion criteria to determine eligibility, each subject will receive a unique study identification number.

Subjects will then be asked relevant medical history questions, including inquiries regarding the presence or absence of COVID-19 and influenza signs and symptoms, vaccine status and current medications taken. Subject demographics including age, sex, race, and ethnicity should also be collected at this time.

Two (2) swabs should be collected for this study: One (1) nasal swab for the Lucira COVID-19 & Flu Test and one (1) nasal swab for composite reference testing. The Lucira COVID-19 & Flu Test study swabs will be collected as directed in the Lucira COVID-19 & Flu Test Quick Reference Instruction (QRI). The reference method swab collection shall be collected by the HCP and prepared in Transport Medium. Each collection may have a maximum of two swabs, including retests, for a maximum of four swabs per visit. Swab specimens required for standard of care testing should be collected prior to the specimens collected for this investigation.

Subject shall be observed during the swabbing collection by the HCP and HCP shall document collection details and any collection issues. Nasal swabs obtained from self-collection will be discarded after having been used for testing per QRI. HCP to interpret and document results.

090177e19dd636e3Approved\Approved On: 25-Jun-2023 03:44 (GMT)

Reference lab shall receive study samples and run samples against FDA cleared/authorized approved SARS-CoV-2 and Influenza A&B Assays. Discrepant analysis samples may be run on a separate FDA cleared/authorized SARS-CoV-2 or Influenza A&B Assays.

Reference testing shall characterize specimens as negative or positive for SARS-CoV-2 and Influenza A&B. Therefore, sensitivity and specificity of the Lucira COVID-19 & Flu Test will be calculated by comparison with the reference methods.

Upon study completion, remnants should be returned to the Sponsor.

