7.3.5 REFERENCE METHOD AND ADDITIONAL TESTING METHODS

Nasal swab samples are important as they provide a natural nasal matrix to conduct analytical reference testing and research. It is imperative that specimens obtained for reference testing are prepared and shipped to the reference laboratory.

Specimens should be stored refrigerated and shipped daily (within 24 hours of collection). Site staff will receive training from the Sponsor or its representative on procedures required to process specimens for shipment to the reference laboratory. Specimens should be shipped with cold packs to maintain the required temperature (2-8°C). Specimen manifest shall accompany the specimens. Inadequate documentation could result in a delay in testing and possible specimen rejection.

Upon receipt, the reference laboratory shall verify the contents of each shipment and communicate any missing or damaged contents to the Sponsor. Aliquots shall be stored for future testing to be performed both during or after the study. All results shall be communicated to the Sponsor or its representative.

Additional testing for discrepant results may be performed to investigate the discrepancy. The discrepant sample, along with some or all non-discrepant samples, may undergo additional testing.

At the end of the study, at Sponsor's discretion, all residual remnant aliquots remaining at the reference laboratory or additional testing laboratories will be sent to the Sponsor or its representative or destroyed.

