8 DATA ANALYSIS AND STATISTICAL CONSIDERATIONS

8.1 SAMPLE SIZE

Clinical agreement specimen enrollment shall target 50 positive Flu A, 30 positive Flu B, and 120 positive COVID-19 until at least 1000 negative subjects are recruited to satisfy specificity requirements of $\leq 98\%$ for COVID-19 and $\leq 95\%$ for Flu A&B.

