8.3 DATA ANALYSIS

All summaries and analyses should be presented in tabular or graphical form.

➤ Analysis Sets

There will only be one analysis set consisting of samples with valid Lucira COVID-19 & Flu Test results and valid reference results. Valid Lucira COVID-19 Test results may be positive or negative for COVID-19. The percentage of the expected result shall be computed individually along with the associated 95% Wilson Score Confidence Interval for each set.

For all invalid Lucira COVID-19 & Flu Test results, one additional specimen collection should be attempted, and the Lucira COVID-19 & Flu Test should be re-run with a new Test Kit. If specimen recollection leads to a valid Lucira COVID-19 & Flu Test result, that valid retest result should be reported. If the Lucira COVID-19 & Flu Test result is "Invalid", then this test result shall be considered completely invalid and therefore non-evaluable.

➤ Prevalence Rate / Expected Values

Study prevalence of SARS-CoV-2 and Influenza A&B should be summarized by counts and percentages

➤ Collection Performance/ Incidence Rate

Relevant study observations should be summarized by counts and percentages:

- Self-Collection
- Assisted Collection

➤ Missing Values

Missing values should not be imputed for any of the study assessments.

➤ Data Exclusions

The following shall result in subjects being removed from final data analysis:

- Subject withdrawals
- Subject does not meet inclusion/exclusion criteria
- Swab specimens were not processed according to protocol
- Missing results
- Excluded by an Event

This analysis should be presented across all study sites and by individual study site.

➤ Efficacy Analysis

Sensitivity and specificity along with their associated 2-sided Wilson Score 95% Confidence Intervals will be estimated for SARS-CoV-2 and Influenza A&B on the Lucira COVID-19 All-In-One Test in comparison to the reference test using the formulas below and a 2 x 2 contingency table ([Table 13.1](#)).

090177e19dd636e3\Approved\Approved On: 25-Jun-2023 03:44 (GMT)

Positive Percent Agreement: $a/(a+c) \times 100$

Negative Percent Agreement: $d/(b+d) \times 100$

Table 13.1: 2 x 2 table for calculation of positive percent agreement and negative percent agreement:

	Reference Positive	Reference Negative	Row Totals
Lucira Positive	a	b	a+b
Lucira Negative	c	d	c+d
Column Totals	a+c	b+d	a+b+c+d

➤ **Invalid Rate**

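### Does the composite reference need a written rule for combining assay results before PPA and NPA can be judged?

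*Combined protocol and SAP*

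**What the plan says.** The synopsis (1.1) says the Lucira test "will be compared with a composite reference method for the detection and differentiation of COVID-19, influenza A and influenza B virus", and section 5.1 repeats the term for the reference swab: "one (1) nasal swab for composite reference testing".

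Other sections describe the comparator differently:
- Section 4 aims at "similar performance to a high complexity lab molecular diagnostic RT-PCR assay(s) with known high sensitivity", which leaves the number of assays open.
- Section 5.1 has the laboratory run FDA cleared or authorized SARS-CoV-2 and Influenza A&B assays and requires each specimen to be characterised as negative or positive. Sensitivity and specificity "will be calculated by comparison with the reference methods".
- On discrepancies, section 5.1 says: "Discrepant analysis samples may be run on a separate FDA cleared/authorized SARS-CoV-2 or Influenza A&B Assays". Section 7.3.5 adds: "Additional testing for discrepant results may be performed to investigate the discrepancy".
- Section 8.3 calculates PPA and NPA against one reference test in one 2 x 2 table (Table 13.1). On who is analysed it says: "There will only be one analysis set consisting of samples with valid Lucira COVID-19 & Flu Test results and valid reference results".

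Section 8.1 "shall target 50 positive Flu A, 30 positive Flu B, and 120 positive COVID-19", with at least 1000 negatives. The section 4 goals are PPA of at least 80% and NPA of at least 98% for COVID-19, and at least 90% and 95% for flu.

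**The concern.** A composite reference normally means several component results and a rule that joins them: any positive, all positive, or two of three. No rule is written, and the words used vary between one test, assay(s) and methods. The reference call decides the column of Table 13.1 into which a specimen falls.

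If components disagree, an any-positive rule tends to lower PPA and protect NPA. An all-positive rule does the reverse, and leaving disagreements out protects both. The rule also changes how many specimens count toward the 120, 50 and 30 positives. The separate assay for discrepant samples is optional, and the term discrepant is not defined. A verdict against the section 4 goals might therefore rest on a choice made after the results are known.

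**Working it through.** **1. What must be true for the gap to matter.** At least two assays per analyte must be run on every specimen, and they must disagree on some. No section states the first condition, and no section gives a rate for the second.

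Section 5.1 names SARS-CoV-2 and Influenza A&B assays, and the plural can mean one assay for each virus group. The synopsis fits this, since its composite serves to detect and differentiate three viruses and so may span analytes. The single reference test in 8.3 fits it too. On this reading no two reference assays report on the same analyte, so there is nothing to combine. Discrepant then means Lucira against the reference, and 7.3.5 gives that extra testing an investigative purpose only.

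**2. What the goals allow at the stated targets.** Section 8.1 gives no power, assumed rate or formula, so its targets cannot be reproduced. Reading the goals on point estimates, the permitted misses are:
- COVID-19 PPA: 0.20 x 120 = 24
- Flu A PPA: 0.10 x 50 = 5
- Flu B PPA: 0.10 x 30 = 3
- COVID-19 NPA: 0.02 x 1000 = 20 false positives
- Flu NPA: 0.05 x 1000 = 50 false positives

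**3. If several assays are run: how many disagreements flip a result?** All starting counts here are assumed. Let x of M specimens positive on all assays be Lucira-positive, and let k disagreeing specimens be Lucira-negative. All-positive PPA is x/M and any-positive PPA is x/(M + k).
- COVID-19: 102/120 = 85.0%. With k = 7, 102/127 = 80.3% (met). With k = 8, 102/128 = 79.7% (missed). From 114/120 = 95.0%, k must reach 23.
- Flu A: 47/50 = 94.0%. With k = 2, 47/52 = 90.4% (met). With k = 3, 47/53 = 88.7% (missed).
- Flu B: 28/30 = 93.3%. With k = 1, 28/31 = 90.3% (met). With k = 2, 28/32 = 87.5% (missed).

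NPA moves the other way. With 15 false positives per 1000, let j Lucira-positive disagreements be counted as reference-negative.
- COVID-19: with j = 5, 985/1005 = 98.01% (met). With j = 6, 985/1006 = 97.9% (missed).
- Flu: even with 20 false positives per 1000, j must reach 32, since 980/1031 = 95.05% and 980/1032 = 94.96%.

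**4. One data set in which the rule decides the verdict.** Assume COVID-19 with 108 positive on both assays (91 Lucira-positive), 12 positive on one only (4 Lucira-positive) and 1000 negative on both (18 Lucira-positive). In the two-of-three row, 6 of the 12 are called positive, 2 of them Lucira-positive.

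| Rule | PPA | NPA |
|---|---|---|
| Any positive | 95/120 = 79.2%, missed | 982/1000 = 98.2%, met |
| Both positive | 91/108 = 84.3%, met | 990/1012 = 97.8%, missed |
| Two of three | 93/114 = 81.6%, met | 986/1006 = 98.0%, met |
| Disagreements left out | 91/108 = 84.3%, met | 982/1000 = 98.2%, met |

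The split arises because the assumed results lie close to both goals. The last row also fits the text poorly. Section 5.1 requires a positive or negative call, and reference disagreement is not among the exclusions listed in 8.3, although the entry for exclusion by an event is open-ended.

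**5. Dependence on the assumptions.** Hold 120 specimens positive on at least one assay, D = 12 of them on one only. Let Lucira detect p1 of the other 108 and p2 of the 12. The any-positive chance of meeting the COVID-19 PPA goal is P[Bin(108, p1) + Bin(12, p2) >= 96]; the both-positive chance is P[Bin(108, p1) >= 87]. The flu A row uses 45 and 5, with thresholds 45 of 50 and 41 of 45.

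| Case | p2 = 30% | p2 = 50% | p2 = 70% | Both positive |
|---|---|---|---|---|
| COVID-19, p1 = 85% | 50% | 72% | 88% | 92% |
| COVID-19, p1 = 90% | 93% | 98% | 99.6% | 99.9% |
| Flu A, p1 = 95% | 46% | 68% | 84% | 93% |

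A higher p2 shifts the effect to NPA and does not remove it. At a true COVID-19 NPA of 98.5%, the any-positive chance is 92%, while the both-positive chance is 69%, 47% and 25% at p2 of 30%, 50% and 70%. For flu at a true NPA of 98% with 2 to 8 disagreements, the chance of meeting 95% exceeds 99.99% under either rule.

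**The case for a change.** The strongest case for a change is that composite, in ordinary use, suggests several assays, and that a single-assay reading makes the word misplaced in 1.1 and 5.1. Either way the text is imperfect. Where assays do disagree there is no neutral default, because each rule favours one goal at the expense of the other. Reference results arrive daily (9.1.4.2), the sponsor compiles both result streams (9.1.4.3), and no section says that the reference call is made blind to the Lucira result. The flu targets are small enough for two or three specimens to matter.

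The textual part stands: the rule is not written and the terms vary. The sensitivity of small flu counts also stands, given the premise of several assays. The alleged harm is not established. It needs a testing scheme that the documents do not describe, disagreement counts they do not give, and results near the goals. Nothing in the plan sends a retest triggered by the Lucira result into Table 13.1. A request to state the rule supplies missing detail without showing that a prescribed rule is wrong or that another would be better.

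**Conclusion.** No change to the plan follows. The comparator is described loosely and its laboratory algorithm is not set out. Section 5.1 does fix the class of assay and require a positive or negative call, and section 8.3 says how the calls are tabulated. Analysts can fill the gap by using the laboratory's qualitative call for each analyte.

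With one assay per analyte the effect is zero. With several, it ranges from negligible (COVID-19 at 95% detection, where 23 Lucira-negative disagreements are needed) to decisive near the goals (2 specimens for flu B at 28/30, 3 for flu A at 47/50, 8 for COVID-19 PPA at 102/120, 6 for COVID-19 NPA at 15 false positives per 1000). Flu NPA is essentially untouched. These figures assume that the goals apply to point estimates, that the flu goal applies to each type, and that the disagreement counts are as chosen here. If the laboratory does run several assays per analyte, a reader of the results should ask which rule was used and when it was fixed.
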